View: 2 Study Objectives & Design

Study Summary**1.0 Funding End Date:****2.0 * Abstract. Please provide a brief description of the study.**

Stroke is the leading cause of neurological disability in the veteran population and problems with arm movement are a major cause of loss of functional ability. The costs of rehabilitation are significant and effectively limit therapy to the first few months after stroke onset. Recent results show clearly that patients with chronic stroke (> 6 months) benefit from intensive arm practice. Robot assisted therapy followed by task related training offers a cost-effective approach to this type of practice that also results in better arm function in daily life. A previous study has shown that it is possible to predict who will benefit from this kind of treatment, specifically what individual characteristics are related to a clinically meaningful improvement in arm movement. This next phase of the study will test whether the prediction method is reproducible and independent of the type of robot being used. It will also expand knowledge of how the brain area most important for movement changes its connections with other brain areas and the muscles in the arm.

3.0 * Describe the study objectives. Please include primary aim and hypothesis, if applicable any secondary aims and hypotheses.

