Chronic upper extremity dysfunction after stroke is a leading cause of disability and has been the target of many therapeutic methods that involve repetitive task practice. Clinical trials of intensive practice-based interventions have demonstrated significant changes in mean impairment in a group, but variable effects among individuals, with clinically significant improvements in only a fraction of the population. This is true of our previous Merit Review study, which showed good mean gains in several areas, and about half of participants having clinically significant changes in the primary outcome of motor impairment. The basis for these variable responses is not known, i.e. we do not know the biological mechanisms that moderate response to these standardized interventions. And while recovery of function is associated with normalization of brain network interactions and task-related brain activation, the causal role of these changes is not well understood. In our current project period, we are continuing to address both issues with construction of a predictive model that uses demographics, functional status, genomics, neurophysiology, neuroanatomy, and other potential biomarkers to predict the likelihood of a clinically significant change in impairment at the end of the intervention.

Our long-range goal is the prescriptive application of intensive task practice to veterans who have suffered a stroke, maximizing the cost-benefit ratio. We therefore plan to externally validate the predictive value of biomarkers as incorporated in the model resulting from our previous chronic stroke robotic rehabilitation trial. We will not only validate the predictive model in a new cohort, we will now quantify the *changes* in functional connectivity of the affected hemisphere's primary motor cortex with other brain areas and with the spinal cord, in order to uncover the mechanisms by which intensive task practice leads to increased motor ability. We will continue to use an effective intervention for individuals with chronic stroke, robotic training

with transition to task practice (Robot + TTT,) now focusing on use of an *exoskeleton platform*, which has already been part of our intervention. We propose the following two specific aims in the proposed renewal of this award:

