1. To validate a predictive model based on baseline measures of biological and functional biomarkers. *Working hypothesis: Baseline factors that include functional and physiological status will predict clinically significant responses to therapy.* Change from use of end-effector and exoskeleton robots to solely exoskeleton will not significantly affect the prediction model. The rationale for the hypothesis is that the effects of assisted repetitive task practice is not dependent on a particular technology but does depend on a biological substrate. Expected outcomes: The predictive model will be externally validated, a receiver operating curve described, and the intervention and model validated on an exoskeleton platform for delivering therapy.

2. To identify the changes in the input and output of the affected primary motor cortex associated with change in motor impairment. *Working hypothesis: Increased input into the motor cortex, increased output from the motor cortex, or both, underlies the treatment effect of repetitive task practice.* Normalization (increase) in connectivity of affected primary motor cortex to other motor brain areas of both sides of the brain will be associated with reduction of motor impairment. In a subpopulation of treatment responders an increased effectiveness of the motor cortex in directly activating muscles will be demonstrated. Expected outcome: The causal role of task practice in changing a brain region's connectivity will be known, with potential uses as a surrogate measure of outcome in rehabilitation trials. Resting state BOLD MRI, transcranial magnetic stimulation, and clinical electrophysiology will be used to provide data regarding the mechanisms of training-related gains.

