When we have completed the above aims, we will have a validated algorithm by which a set of baseline variables (biomarkers) can be used to inform both the clinician and patient regarding the likelihood of successful training, in an appealing exoskeleton robotic rehabilitation platform, for upper extremity disability in the chronic period after stroke. This algorithm can be modified to consider those biomarkers that are more practical in VA clinical settings. We will also extend mechanistic knowledge about the response to intensive training on brain connectivity, which has been noted to be altered after stroke and which may relate to learned non-use of the affected limb and loss of spinal response to descending input. We will have new efficacy data on the use of assisted mass practice followed by assisted task practice on multiple dimensions of functioning and disability, including use of the arms in daily life.

4.0 * Provide a summary of the background of the study, and explain how this research will contribute to existing knowledge. Describe previous studies that provides a basis to show that the proposed research can be carried out without undue risk to human subjects.

Stroke is the leading cause of long-term disability [1] costing an estimated \$38.6 billion a year [2] and stroke-related disability is becoming more prevalent [3], even as overall rate of stroke is in slight decline. Recent evidence indicates that the brain can remodel after stroke, even years later, through neuroplasticity (including changes in excitability and synaptic strength) and synaptogenesis [4-6]. Behavioral remodeling also occurs and allows compensatory movement patterns to accomplish

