task goals [7-9]. Interventions incorporating strategies of task specificity, challenge, and repetition appear to be key factors in promoting these two types of remodeling and are central elements in rehabilitation of motor weakness following stroke [11]. Since our initial project period, the value of robot-assisted therapy to improve upper extremity function has become more established but there are still questions about many aspects of implementation, including patient selection, dose, and type of treatment [12]. There are two basic types of rehabilitation robots, *endeffector*, in which the patient engages with the tip of the limb, and *exoskeleton*, in which a powered framework encloses the limb. Both types have demonstrated efficacy [13] with some potential advantage in full use of exoskeleton capabilities in training joint coordination [14], and we have used both types in our ongoing study. Robot-assisted and other types of upper extremity treatment studies in chronic stroke report relatively modest *average* gains in motor function that typically fail to translate into meaningful change in everyday use of the paretic arm [15]. This has prompted us to directly address issues of predicting response, promoting and measuring translation to daily use and determining optimal scheduling for that therapy. Therefore, there is now a critical need for research that: 1. predicts response to hybrid robotic and functional task oriented therapies in chronic stroke and 2. determines the brain mechanisms of response to such therapies so that we better understand why such therapies work for some, but not all, stroke survivors.

5.0 * Describe the overall significance of the research in terms of the problem to be studied and potential findings, as well as its relevance to the care of veterans, the VAPHS, and the VHA:

Importance and Impact

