If yes, please indicate which time points are considered usual care and which are considered research.

2.4 If there is more than one standard, does VAPHS limit which one is followed (e.g. warfarin use for atrial fibrillation vs. one of the newer anticoagulants).
 Yes **No**

If yes, please explain:

3.0 * **Does clinical expertise need to be enlisted?**
 Yes **No**

If yes, please provide the provisions for enlisting the services of a clinician with appropriate expertise and privileges to perform duties, if the investigator is not a clinician [i.e. reviewing the data, adverse events, and new study findings; also making required decisions to protect the health of the subject (e.g., stopping the participant’s involvement in the study or determining when to notify the subject or the subject’s health care provider of information that may affect the health of the subject)]:

4.0 Please upload any surveys, questionnaires, and data collection forms.

Document	Description	Version Number
View ARAT Scoring(0.01)		0.01
View Demographics(0.01)		0.01
View Dynamometry and ROM Scoring(0.01)		0.01
View Finger Assessment Form(0.01)		0.01
View Fugl-Meyer Scoring(0.01)		0.01
View Inclusion Exclusion Checklist(0.01)		0.01
View Medical History Form(0.01)		0.01
View Stroke History Form(0.01)		0.01
View Stroke Impact Scale(0.01)		0.01
View Wolf Scoring(0.01)		0.01

ID: Pro00003161

View: 4.1 Research study methods: analysis Plan

1.0 * **Please describe the analysis plan for the study** (*it is acceptable to refer to the sponsor/multi-site protocol for section if applicable*):

Analysis Plan for Aim #1.

We will determine the receiver operating curve (ROC, sensitivity vs 1-specificity) of the predictive model for the primary outcome, a (positive) change in FMA of greater than four points at 12 weeks. (A five-point change in FMA is a MCSD [34].) The ROC will be compared to the SRT4 model [35]. With our proposed sample size of 64 subjects and 12% attrition rate, we expect to have 57 subjects completing the study, a validation set of similar size to the original set from which the model was derived.

Further analysis, validation and refinement of the predictive model will be performed using the random decision forest technique [36]. This would also result in an algorithm like the PREP [30] that can be used for step-wise decision-making about embarking on the 12-week program of robot+TTT.

Analysis Plan for Aim #2.

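### Comparing the SRT5 ROC curve with the SRT4 model cannot establish the part of the Aim 1 hypothesis that prediction does not depend on robot type

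*Combined protocol and SAP*

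**What the plan says.** All references are to the combined protocol and SAP.

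- **Purpose.** The abstract (View 2, item 2.0) says: "This next phase of the study will test whether the prediction method is reproducible and independent of the type of robot being used".
- **Aim 1** (View 2, item 3.0) is headed as validation of a predictive model. Its working hypothesis is "Baseline factors that include functional and physiological status will predict clinically significant responses to therapy", followed by "Change from use of end-effector and exoskeleton robots to solely exoskeleton will not significantly affect the prediction model". The expected outcomes are external validation, a described ROC curve, and a model validated on an exoskeleton platform.
- **Cohorts.** The objectives say "We will not only validate the predictive model in a new cohort". On robots in the earlier work, the background (View 2, item 4.0) says "we have used both types in our ongoing study". SRT5 is one-arm, and all participants get the same intervention (View 1.5; View 4).
- **Analysis** (View 4.1, Analysis Plan for Aim #1). The ROC curve of the model is determined in SRT5; then "The ROC will be compared to the SRT4 model [35". Reference 35 (View 14) is titled as a method for two or more correlated ROC curves. A random-forest refinement follows.
- **Size** (View 6, item 4.0). About 57 completers are expected. The justification is the precision of a single AUC.

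**The concern.** The sentence on the comparison does not say what is compared with what, and it is the only analysis that could bear on robot type. The hypothesis is worded as the absence of a significant effect, so a non-significant SRT5–SRT4 difference would naturally be reported as confirming it. With cohorts of this size, that result is likely even if the model loses all discrimination on the new platform. A claim that prediction is independent of robot type could then enter the literature, and the decision algorithm promised to clinicians and patients, without evidence behind it.

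**Working it through.** **Inputs.** SRT5 n = 57 (View 6). AUC 0.70 with 33% responders is the preliminary situation given there. The objectives give a second responder figure, "about half of participants having clinically significant changes in the primary outcome of motor impairment", so I use 33% (19 responders, 38 non-responders) and 50% (28 and 29). SRT4 size is not stated: View 4.1 calls the validation set similar in size to the derivation set (taken as 57), and View 6.1.1 says nearly 40 completed the previous version (taken as 40). Assumed: two-sided 0.05, the same responder share in both cohorts, and AUC 0.80 as an upper case.

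**Step 1: the plan's own figure.** The method is Hanley–McNeil, the plan's reference 10:

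SE² = [A(1−A) + (n₁−1)(Q₁−A²) + (n₂−1)(Q₂−A²)] / (n₁n₂), with Q₁ = A/(2−A) and Q₂ = 2A²/(1+A).

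At A = 0.70, Q₁ = 0.5385 and Q₂ = 0.5765.
- 33%: (0.21 + 18×0.0485 + 37×0.0865)/722 = 0.00593, SE = 0.0770.
- 50%: (0.21 + 27×0.0485 + 28×0.0865)/812 = 0.00485, SE = 0.0697.

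At A = 0.80 the SEs are 0.0673 and 0.0595; at 0.90 they are 0.0501 and 0.0430. This matches the plan's statement that the SE is below 0.07 except at AUC 0.7 with 33% responders.

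**Step 2: reading 1, SRT5 against SRT4.** Separate subjects mean zero covariance, so SE(diff) = √(SE₅² + SE₄²) and the 95% half-width is 1.96 × SE(diff). At a true AUC of 0.70 in both:

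| SRT4 n | Responders | SE₅ | SE₄ | SE(diff) | Half-width |
|---|---|---|---|---|---|
| 57 | 33% | 0.0770 | 0.0770 | 0.1089 | 0.213 |
| 57 | 50% | 0.0697 | 0.0697 | 0.0985 | 0.193 |
| 40 | 33% | 0.0770 | 0.0931 | 0.1208 | 0.237 |
| 40 | 50% | 0.0697 | 0.0833 | 0.1086 | 0.213 |

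With 57 per cohort, two equal AUCs of 0.70 would leave a fall to about 0.49–0.51 inside the interval. If the SRT4 AUC were known exactly, SRT5 alone would still give 1.96 × 0.0770 = 0.151 or 1.96 × 0.0697 = 0.137.

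**Step 3: power for a fall from 0.70 to 0.50, 57 per cohort.** The SE at AUC 0.50 is 0.0818 (33%) or 0.0772 (50%).
- 33%: 0.20/√(0.0818² + 0.0770²) = 0.20/0.1124 = 1.78; power Φ(1.78 − 1.96) = 0.43.
- 50%: 0.20/0.104 = 1.92; power Φ(1.92 − 1.96) = 0.49.

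With SRT4 n = 40, power is 0.365 and 0.42.

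**Step 4: fall detectable with 80% power, 57 per cohort**, using the SE at the lower AUC for SRT5. From 0.70 it is 0.307 (33%) or 0.289 (50%), that is, to about 0.39–0.41, below chance. From 0.80 it is 0.297 or 0.273.

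**Step 5: confounding.** On reading 1, robot type differs only between cohorts. The contrast is also mixed robots against exoskeleton only, not one type against the other. A larger sample would not separate robot from cohort. If the SRT4 AUC comes from the data that built the model, it may also be optimistic, so some fall is possible with no robot effect at all.

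**Step 6: reading 2, two models on the same SRT5 subjects** (for example the SRT4 model and its random-forest refinement). The curves are correlated and reference 35 fits. But all subjects are in the exoskeleton-only programme, so the comparison is between models and carries no information on robot type.

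**The case against.** Aim 1 is validation, not a test of robots. Robot independence is one sentence of the hypothesis and one line of the abstract, and the expected outcomes already speak of a model validated on an exoskeleton platform. That stands, and it limits the point to one part of the aim. A reader might infer that Aim 1 as a whole fails or that 57 is too few. The documents do not support this: the ROC curve in SRT5 is the first planned analysis, and sizing it on the SE of the AUC is sound and reproduces.

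The comparison is also not worthless. A large fall in AUC would count against the hypothesis, so it can contradict the hypothesis even though it cannot confirm it.

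The mismatch with reference 35 rests on its title and on reading 1; on reading 2 there is none. It is a matter for clarification, not proof of a wrong method.

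The objectives close with "When we have completed the above aims, we will have a validated algorithm", and a reader might infer that the plan is defective without a numerical pass mark for validation. A plan sized for estimation can report an AUC with its interval and no pass/fail rule, so a floor is a preference.

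Finally, this is an IRB portal form. The uploaded grant application is not visible and may define the comparison. It could settle which reading is meant, but on neither reading described here would that remove the problem.

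**Conclusion.** The point holds for the robot-independence part of Aim 1 and should be fixed before analysis. On either reading, the stated comparison cannot establish that prediction is independent of robot type. Under the cohort reading with 57 per cohort and AUC 0.70, the difference carries a 95% half-width of about 0.19–0.21 (0.21–0.24 if SRT4 had 40). A complete loss of discrimination would be missed more often than not. The 80%-power detectable difference is about 0.27–0.31 for a starting AUC of 0.70–0.80. These sizes depend on the assumed SRT4 size, responder share, AUC and two-sided 0.05 level. The confounding of robot type with cohort depends on none of them. The validation of the model itself is not called into question.

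**What to change.** 1. Report the AUC of the unchanged SRT4 model in SRT5, with its 95% confidence interval, as the validation result.
2. If SRT5 is compared with SRT4, say so, and report the unpaired AUC difference with its 95% confidence interval (zero covariance). Label the SRT4 AUC as optimism-corrected or uncorrected.
3. Keep the correlated-curve method of reference 35 for models scored on the same SRT5 subjects, with the random-forest refinement scored out-of-bag or cross-validated.
4. In the abstract and in the Aim 1 hypothesis, replace the test of robot independence with a description of model performance on an exoskeleton platform, in line with the expected outcomes. State that a non-significant difference is not evidence of independence from robot type.

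A numerical floor, such as a lower confidence limit above 0.50, is optional and the sponsor's choice.

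**Cost.** Changes to the analysis plan and aim wording only; no added participants, visits or measurements. The study can no longer claim independence from robot type from this comparison. An optimism correction needs SRT4 data that these documents do not show; without it, the uncorrected label serves.

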The primary analysis will be correlation between change in physiological parameters (e.g. affected M1 connectivity, recruitment curve slope) and change in FMA. Analysis of H-reflex changes will be compared to recruitment curve changes to rule out a general change in lower motor neuron excitability. Secondly, there will be correlations of these parameters at baseline with baseline motor function measures. A more detailed analysis of the MRI data will also examine individual interregional connections to determine whether any of them are more sensitive to the intervention than others. There will be exploration of whether the predictive model also predicts changes in physiological measures, which could lead to more efficient studies in the future.

ID: Pro00003161

View: 5 Sub-Studies

- 1.0** *** Is there a sub-study or are there sub-studies associated with this study?**
There is no sub-study associated with this study.

ID: Pro00003161

View: 6 Study Population Summary

Study Population Summary

1.0 * What is the maximum number of subjects you plan to enroll at VAPHS?
80

2.0 * Do you plan on enrolling patients into different categories:
 Yes No

If yes, please explain:

3.0 If this is a multi-site study, indicate the projected total subject accrual:
70

4.0 * Please provide a justification for the sample size:

Based on our record of recruitment and design feasibility, we propose to enroll 64 participants. Our current 12-week study has an attrition rate after enrollment of 12% so we anticipate completing about 57. We verify that with our sample size of 57, we will be able to estimate the area under the Receiver operating characteristic (ROC) curve (AUC) with an adequate precision (that is, the standard error is reasonably small). The AUC is an important measure to describe the performance of a predictive model for a binary outcome such as the change in FMA of greater than 4. The table below displays the standard error (SE) of the estimated AUC for several values of the true AUC and different prevalence of responders [10]. The SE is less than 0.07 in all cases except when AUC is 0.7 and the proportion of responders is only 33%. (This is the current situation in the preliminary analysis, providing an upper bound on our AUC measure.)

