4.0 If there are any age, ethnic, language, or gender-based exclusion criteria, including the exclusion of any pregnant or lactating women, or those of child-bearing potential, please provide justification:

Participants must be English speaking to ensure that all study procedures and interventions are understood and performed safely.

5.0 Please specify why vulnerable subjects and/or special populations will not be enrolled:**6.0 With some exceptions as listed in VHA Handbook 1200.05, incompetent subjects cannot be enrolled in VAPHS approved research. Specify that you will not enroll incompetent subjects and the general rules to be used in making that determination:**

Incompetent subjects will not be enrolled in this study because they would not meet the inclusion/exclusion criteria for the study.

ID: Pro00003161

View: 6.1.1 Non-Veterans

Non-Veterans

1.0 * Target number of participants:
25

2.0 * Describe why you cannot complete enrollment in this study without the use of Non-Veterans:

As stated in our study objectives, our long-range goal is the prescriptive application of intensive task practice to individuals who have suffered a stroke, maximizing the cost-benefit ratio. Our predictive model must be validated with a large and heterogeneous group of subjects having varied demographics, functional status and neurophysiology. Considering the inclusion/exclusion criteria, it is possible that we would not recruit a sufficient number of veteran subjects required to complete the proposed study in accordance with 38 CFR 17.45 and 38 CFR 17.92. For eligible subjects, their stroke must be their main health deficit. Participants may be excluded from the study if they have orthopedic and/or joint problems in the arm affected by their stroke. They cannot have any other injuries to the brain such as traumatic brain injury diagnosis. Therefore, we will recruit non-veteran subjects in order to achieve our goal of validating our predictive model. Nearly 40 subjects have completed the previous version of the study without any major study-related adverse events, therefore we expect future participants will have a low likelihood of injury from the study procedures.

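### Aim 1 compares the new ROC with an SRT4 benchmark that has no stated size, interval or optimism correction, so a fall due to overfitting could be read as an effect of the robot change

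*Combined protocol and SAP*

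**What the plan says.** The analysis plan (View 4.1, Aim 1) will determine the ROC of the predictive model for an FMA gain of more than four points at 12 weeks and compare it with the SRT4 model. On size it says: "With our proposed sample size of 64 subjects and 12% attrition rate, we expect to have 57 subjects completing the study", and describes that as "a validation set of similar size to the original set from which the model was derived". It gives no number for the derivation set.

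The only count for the earlier study is in View 6.1.1 (Non-Veterans, item 2.0): "Nearly 40 subjects have completed the previous version of the study without any major study-related adverse events". This supports an argument about safety and recruitment; it is not offered as the N of the model.

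The sample size justification (View 6, item 4.0) gives standard errors for the AUC in the new cohort only. It links the setting of AUC 0.7 with 33% responders to a preliminary analysis, but does not say how any AUC there was obtained. The study objectives (View 2, item 3.0) state that moving from two robot types to an exoskeleton alone is not expected to affect the model significantly.

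**The concern.** Aim 1 is an external validation, and the SRT4 ROC is the only named yardstick. The comparison therefore depends on how firm that yardstick is, and the plan says nothing about this beyond the remark on similar size.

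An AUC computed on the data that fitted a model is biased upwards, and a validation AUC for the same fixed model is not. Setting one against the other builds in an expected fall even if nothing about patients or robots has changed. Because the plan also has a hypothesis about the robot change, an ordinary fall could be read either as a device effect or as failed validation. The candidate inputs listed in the objectives are broad (demographics, function, genomics, neurophysiology, neuroanatomy and other biomarkers), and the derivation set is small on any reading.

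**Working it through.** **Inputs.** 64 enrolled with 12% attrition (Views 4.1 and 6). Close to 40 earlier completers (View 6.1.1), taken as 39. Responders 33% (View 6, item 4.0) or about half (View 2, item 3.0). AUC 0.70, the setting that View 6 links to its preliminary analysis. The number of predictors is not given; I assume 3, 5 and 8.

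**The plan's own figures.** 64 × 0.88 = 56.3, which fits about 57. The Hanley-McNeil formula, which the plan cites, is

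SE² = [A(1−A) + (n1−1)(Q1−A²) + (n0−1)(Q2−A²)] / (n1·n0), with Q1 = A/(2−A) and Q2 = 2A²/(1+A).

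At n = 57 it gives:

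| AUC | 33% responders | 50% responders |
|---|---|---|
| 0.7 | 0.077 | 0.0697 |
| 0.8 | 0.067 | 0.060 |
| 0.9 | 0.050 | 0.043 |

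This agrees with the statement that the SE is under 0.07 except at AUC 0.7 with 33% responders. The plan's table itself is not visible in the copy reviewed.

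**Precision of the SRT4 AUC.** At A = 0.70, Q1 = 0.5385 and Q2 = 0.5765, so Q1−A² = 0.0485 and Q2−A² = 0.0865.

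- 57 participants (19 responders, 38 not): SE² = (0.21 + 18 × 0.0485 + 37 × 0.0865)/722 = 0.00593, SE = 0.077.
- 39 participants (13 responders, 26 not): SE² = (0.21 + 12 × 0.0485 + 25 × 0.0865)/338 = 0.00874, SE = 0.093.

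**Precision of the difference.** The cohorts are separate, so the variances add.

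- 57 and 57: √(0.00593 + 0.00593) = 0.109; 95% half-width 1.96 × 0.109 = 0.21.
- 57 and 39: √(0.00593 + 0.00874) = 0.121; half-width 0.24.
- With 50% responders the half-widths are 0.19 (57 and 57) and 0.21 (57 and 40).

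**Optimism of an in-sample AUC.** I simulated derivation sets with 33% responders and a best attainable AUC of 0.70, fitted a logistic model, and took the apparent AUC minus the true AUC of the fitted weights (3,000 sets per setting):

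| Predictors (assumed) | n = 57 (19/38) | n = 39 (13/26) |
|---|---|---|
| 3 | 0.060 | 0.088 |
| 5 | 0.105 | 0.147 |
| 8 | 0.162 | 0.215 |

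A second simulation used a linear discriminant with one true predictor. It gave 0.063, 0.105 and 0.160 at n = 57, and 0.085, 0.140 and 0.209 at n = 40, so the result does not hinge on the classifier.

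**Size relative to the comparison.** At n = 57 the built-in fall is 0.060/0.213 = 0.28 to 0.162/0.213 = 0.76 of a 95% half-width. At n = 39 it is 0.088/0.237 = 0.37 to 0.215/0.237 = 0.91.

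**The case against.** A reader might infer that the plan contradicts itself: a derivation set put at about 57 in one place and about 40 in another. The documents do not establish that. The figure of nearly 40 is never called the derivation set, and the earlier work is described in places as unfinished: "In our current project period, we are continuing to address both issues with construction of a predictive model", and "Our current 12-week study has an attrition rate after enrollment of 12% so we anticipate completing about 57". If the figure is a running count and the model uses the full earlier cohort, the two statements are compatible. Other text calls the trial previous and the model its result, so its status is unclear, but that is not a contradiction. A grant application is listed as uploaded (View 1.3) and may state the number; it was not available here.

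A reader might also infer that the SRT4 AUC is less precise than presented. No SRT4 precision is presented, so that does not hold either. Nor is the sample size calculation affected: it rests on recruitment, feasibility and the standard error at 57, and it reproduces.

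The effect of size alone is small: the half-width moves from 0.21 to 0.24, and the difference between the two sizes adds only about 0.03 to 0.05 to the optimism. Finally, the documents do not say that the SRT4 AUC is in-sample. The sponsor may already hold a cross-validated one.

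All of this stands. It leaves one point untouched: whether the derivation set is 40 or 57, the plan does not say which SRT4 AUC is the benchmark, and an uncorrected one would bias the comparison.

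**Conclusion.** The point holds as a cheap improvement, not as a demonstrated error. The benchmark for the one named Aim 1 comparison is unspecified. If it is an in-sample AUC, it is too high by roughly 0.06 to 0.21, and the SRT5 minus SRT4 difference is biased towards a false fall.

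The direction is firm for any model fitted to a set of this size. The amount is illustrative, because it rests on an assumed 3 to 8 predictors, a best AUC of 0.70, 33% responders and no internal correction. The comparison is imprecise in any case, with a half-width of 0.21 to 0.24 under those conditions, and the plan shows no precision for it. Whether the remark on similar size is accurate cannot be settled from the documents.

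**What to change.** In the Aim 1 analysis plan (View 4.1):

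1. Define the benchmark as the bootstrap optimism-corrected (or leave-one-out) SRT4 AUC with its own confidence interval. Repeat every model-building step, including any variable selection, inside the resampling.
2. Report the SRT5 minus SRT4 difference with an interval for two separate cohorts, based on their actual sizes and responder counts, and read the robot hypothesis from that interval.
3. Replace the remark on similar size with the number of SRT4 participants and responders used to fit the model, and say how that relates to the count in View 6.1.1.

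The cost is a few sentences and a re-analysis of existing SRT4 data, with no new participants or procedures. The downside is that the benchmark AUC and the stated precision of the comparison will look somewhat less favourable.
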